The treatment emergent adverse events as of the cutoff date of September 6, 2016, regardless of BGJ398 relationship, that occurred in 20% or more of patients are: increases in phosphorus levels (covered by the preferred terms of hyperphosphatemia, 57.5%, and blood phosphorus increased, 9.2%), constipation (39.6%), decreased appetite (36.2%), fatigue (34.3%), stomatitis (33.3%), nausea (31.4%), blood creatinine increased (28.5%), diarrhea (27.5%), alopecia (26.1%), dry mouth (23.7%), vomiting (20.8%), and anemia, 20.3%. Approximately 58 percent of patients (120/207) experienced at least one grade 3 or 4 event regardless of the relationship to BGJ398. Grade 3 or 4 events that occurred in at least 5% of patients were lipase increased (6.8%) and alanine minotransferase increased (5.3%). Overall, most adverse events reported have been mild to moderate in severity, reversible, and unrelated to BGJ398.

Hyperphosphatemia has been seen in the majority of patients treated at doses of 100 mg qd and higher and is a pharmacodynamic (PD) marker of on-target FGFR pathway inhibition. Renal tubular phosphate secretion and reabsorption are controlled through the FGFR1 pathway. Inhibition of this pathway leads to inability to secrete phosphate and secondary elevations in FGF23. The hyperphosphatemia has been managed in the Phase 1 study by dietary phosphate restrictions, phosphate lowering therapy, and drug interruptions and dose reductions, which led to the introduction of the alternate 3 weeks on/1 week off drug schedule. Preliminary safety data with this schedule suggest improved tolerability and compliance with drug administration (e.g. fewer dose interruptions during cycle 1), though dose reductions in later cycles of therapy are not uncommon. As of a March 15, 2014 data cut off, seventeen of 25 patients (68%) who received BGJ398 on the 3 week on/1 week off schedule experienced elevated phosphorous and only 4 patients (16%) required cycle 1 interruptions or reductions. In contrast, 41 of 47 patients (87%) on the continuous dosing cycle experienced serum phosphorous elevations. Twenty patients (43%) required cycle 1 dose interruptions and 13 patients (28%) required dose reductions during cycle 1.

Preliminary analysis does not show any effect of BGJ398 on QTc prolongation. Please refer to the BGJ398X Investigator Brochure for additional information.

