 - Acute myelogenous leukemia (AML) by World Health Organization (WHO) classification or acute lymphoblastic leukemia (ALL) relapsed or refractory to standard chemotherapy; unsuitable for standard chemotherapy or unwilling to undergo standard chemotherapy. Philadelphia chromosome (Ph) positive ALL eligible if failed prior tyrosine-kinase inhibitor therapy.
 - Age > 60 years with AML not candidates for or have refused standard chemotherapy, excluding patients with acute promyelocytic leukemia (APL) or with favorable cytogenetic abnormalities [inv16, t(8;21)].
 - For patients with Chronic Myeloid Leukemia (CML) only accelerated and blast phase CML will be allowed.
- e. **TIO diagnosis:** refer to inclusion 3b
- 11. Patient has an Eastern Cooperative Oncology Group (ECOG) performance status ≤ 1 ([Appendix N](#)).
- 12. Patient has a life expectancy of at least 16 weeks
- 13. All patients must have adequate bone marrow as described below:
 - a. Absolute Neutrophil Count (ANC) $\geq 1.0 \times 10^9/L$ (not applicable for leukemia patients)
 - b. Platelets (PLT) $\geq 75 \times 10^9/L$ (no platelet transfusion within past 14 days) (not applicable for leukemia patients)
 - c. Hemoglobin (Hgb) $\geq 9 \text{ g/dl}$ (not applicable for leukemia patients)
 - d. For Leukemia patients, peripheral blast counts $< 50,000 \text{ blasts/mm}^3$
 - e. International Normalized Ratio (INR) ≤ 1.5
 - f. For Leukemia patients, peripheral blast counts $< 50,000 \text{ blasts/mm}^3$
- 14. All patients must have adequate organ function defined as described below:
 - a. Potassium, calcium inorganic phosphorous and magnesium within normal limits (WNL). Supplementation is allowed to meet eligibility requirements
 - b. Serum creatinine $\leq 1.5 \times \text{ULN}$
 - c. Alanine aminotransferase (AST) and/or aspartate aminotransferase (ALT) $\leq 2.5 \times$ upper limit of normal range (ULN) or $\leq 5 \times \text{ULN}$ if liver metastases are present
 - d. Total serum bilirubin within normal range (or $\leq 1.5 \times \text{ULN}$)
 - e. Serum amylase and lipase \leq upper limit of normal (ULN)
 - f. Proteinuria \leq Grade 2 (dipstick or 24hrs urine analysis) (Not applicable for Urothelial cell carcinoma patients)

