6.3 Dose modifications

6.3.1 Dose modification and dose delay

For patients who do not tolerate the protocol-specified dosing schedule, dose adjustments are permitted in order to allow the patient to continue the study treatment. Any changes in BGJ398 administration must be recorded on the Dosage Administration Record eCRF.

BGJ398 dose modification guidelines are described in [Section 6.3.2](#). Any planned variance from these guidelines in the view of the patient safety must be previously discussed with the sponsor unless there is an urgent need for action.

All dose modifications, interruptions or discontinuations must be based on the worst preceding toxicity as graded by the NCI Clinical Toxicity Criteria for adverse events (NCI-CTCAE version 4.03). Once a dose has been reduced during a treatment cycle, re-escalation will not be permitted during any subsequent cycle.

If the administration of BGJ398 is interrupted for reasons other than toxicity, then treatment with the study drug may be resumed at the same dose. The same applies if the patient experienced an unacceptable toxicity not specifically described in [Table 6-3](#) or [Section 6.3.4](#), provided this toxicity resolved to \leq CTCAE grade 1, unless otherwise specified.

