6.3.2 Permitted study treatment adjustments for BGJ398

For patients who are unable to tolerate the protocol-specified dosing schedule, dose reductions or interruptions are permitted to manage drug-related toxicities. For patients with TIO diagnosis additional dose reductions may be allowed upon Novartis approval.

- When dose reduction is necessary, the dose of BGJ398 may be reduced to 100 mg, QD.
- If an additional dose reduction is required, BGJ398 may be reduced to 75 mg, QD.
- Once the BGJ398 dose is reduced it cannot be re-escalated.
- All dose reductions should be based on the worst preceding toxicity.

- Patients are allowed only 2 dose reductions (to 100 mg and 75 mg) as specified in ([Table 6-2](#)).

Table 6-2 BGJ398 dose modifications

BGJ398 Dose Level	BGJ398 Dose
Starting dose level (0)	125 mg po QD (3 weeks on, 1 week off in a 28 day cycle)
Dose level – 1	100 mg po QD (3 weeks on, 1 week off in a 28 day cycle)
Dose level – 2	75 mg po QD (3 weeks on, 1 week off in a 28 day cycle)

- A third or subsequent reduction (to 50 mg, QD) in dose may be allowed if the patient is clearly benefiting from study treatment (i.e., stable disease, partial response, or complete response) but is experiencing adverse events that prevent continued treatment at the already reduced dose. For patients with TIO diagnosis without measureable/evaluable disease, the assessment criteria for additional dose reduction will be the tumor associated improvement of metabolic parameters. A third reduction or subsequent dose reduction requires approval from Novartis.

Patients whose treatment is interrupted or permanently discontinued due to an adverse event including abnormal laboratory values must be followed at least once a week for 4 weeks, and subsequently at 4-week intervals, until resolution or stabilization of the event, whichever comes first. The maximum time allowed for treatment interruption due to toxicity is 14 days (2 weeks) from the intended dosing day. If interruption is > 14 days, the patient must be discontinued from the study treatment. However, the patient will continue to be followed for toxicity. Dose interruptions should be reported on the appropriate Dosage Administration eCRF.

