Grade 4	Discontinue patient from study treatment. Patients with total bilirubin \geq Grade 1 (any duration) should have fractionation of bilirubin into total/direct or indirect/direct components and any additional work-up as clinically indicated by these results. Follow-up of hyperbilirubinemia should proceed as per the guidelines mentioned above, irrespective of the results of fractionation.
AST or ALT	
Grade 3	Hold dose of BGJ398 until resolved to CTCAE Grade \leq 1 or baseline (repeat parameter at least twice a week and as indicated), then: 
 • If resolved within \leq 7 days, maintain dose level of BGJ398. • If resolved within > 7 days, \downarrow 1 dose level of BGJ398. Discontinue patient from study treatment.
Grade 4	
AST or ALT and Bilirubin	
AST or ALT $>$ 3.0 – 5.0 x ULN and total bilirubin $>$ 2.0 x ULN without liver metastasis or evidence of disease progression in the liver	Hold dose of BGJ398 until resolved to CTCAE Grade \leq 1 
 • If resolved within \leq 7 days, \downarrow 1 dose level of BGJ398. • If resolved within > 7 days, discontinue patient from study treatment. Discontinue patient from study treatment.
AST or ALT $>$ 5.0 x ULN and total bilirubin $>$ 2.0 x ULN	

Worst Toxicity CTCAE v4.03 Grade (unless otherwise specified)	Recommended Dose Modifications any time during a cycle of therapy
Laboratory / Metabolic disorders	
Asymptomatic amylase and/or lipase elevation	
Grade 3 (> 2.0 - 5.0 x ULN)	
 • Hold dose of BGJ398 until resolved to CTCAE Grade ≤ 2. • ↓ 1 dose level of BGJ398
Grade 4 (> 5.0 x ULN)	
For recurrent grade 3 asymptomatic lipase or amylase elevation despite dose reduction, drug should be held and continuation of therapy should be discussed with the medical monitor following resolution to ≤ grade 2.
 
For any grade 4 asymptomatic lipase or amylase elevation, drug should be held and continuation of therapy should be discussed with the medical monitor following resolution to ≤ grade 2.

	
Note: A CT scan or other imaging study to assess the pancreas, liver, and gallbladder should be performed as clinically indicated within 1 week of the first occurrence of any CTCAE ≥ Grade 3 amylase and/or lipase.

Grade 4 (> 5.0 x ULN)	Discontinue patient from study treatment
Hyperphosphatemia	Hold BGJ398 dose until resolved to serum phosphorus ≤ 5.5 mg/dL:

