7.1.3.2 Criteria for premature patient withdrawal (EOT phase completion)

Patients **may** voluntarily withdraw from the study or be dropped from it at the discretion of the investigator or by the sponsor at any time.

Premature patient withdrawal refers to the point/time when the patient exits from the study treatment prior to the planned completion of all study treatment administration and/or assessments; at this time, all study drug treatment is discontinued and no further assessments are planned, unless the patient will be followed for progression and/or survival.

Patients may be withdrawn from the study treatment if any of the following occur:

- Adverse Event
- Lost to follow-up
- Non-compliance with study treatment
- Physician decision
- Pregnancy
- Progressive Disease
- Protocol deviation
- Study terminated by sponsor
- Subject/guardian decision
- Death
- In addition to the general withdrawal criteria, the following **study specific criteria** will also require study treatment discontinuation:
 - Adjustments to study treatment that result in discontinuation. Please refer to [Section 6.3](#).
 - Use of prohibited medication. Please refer to [Section 6.4.3](#).

- Interruption of study treatment for > 14 days, regardless of reason, from the intended day of the next scheduled dose

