7.2.2.6.2 Biochemistry

Biochemistry tests are to be performed by the local laboratory at screening, Days 1, 8, 15, 21 of Cycle 1 and Days 1 and 15 of Cycles 2, at Day 1 of each subsequent cycle and at EOT according to the Visit Schedule outlined in [Table 7-1](#). The full biochemistry panel includes blood urea nitrogen (BUN), creatinine, uric acid, sodium, magnesium, potassium, glucose, calcium, inorganic phosphate [Pi], LDH, total protein, albumin, bicarbonate, amylase, lipase, total cholesterol, high density lipoprotein (HDL), low density lipoprotein (LDL), and triglycerides. Additionally liver function test including AST/SGOT, ALT/SGPT, GGT, alkaline phosphatase, total, direct and indirect bilirubin will be measured.

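### Protocol Table 6-3 gives two incompatible actions for grade 4 asymptomatic amylase or lipase elevation: hold and discuss restarting, or discontinue

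*Protocol*

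**What the plan says.** Protocol Table 6-3, in its laboratory and metabolic block, has a heading for amylase or lipase elevation without symptoms. Under it stand:

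- a grade 3 rule (above 2.0 and up to 5.0 x ULN): hold until grade 2 or lower, then reduce by one dose level;
- a rule for grade 3 that recurs despite the reduction: hold, and discuss continuation with the medical monitor after recovery;
- a grade 4 sentence: "For any grade 4 asymptomatic lipase or amylase elevation, drug should be held and continuation of therapy should be discussed with the medical monitor", again after recovery to grade 2 or lower;
- a note on imaging the pancreas, liver and gallbladder;
- a further row: "Grade 4 (> 5.0 x ULN) Discontinue patient from study treatment".

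The next entry in the table is hyperphosphatemia.

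Section 6.3.1 adds a general clause: "Any planned variance from these guidelines in the view of the patient safety must be previously discussed with the sponsor", unless urgent action is needed. Section 6.3.2 limits interruptions: "The maximum time allowed for treatment interruption due to toxicity is 14 days (2 weeks) from the intended dosing day". Section 7.1.3.2 lists as a reason for stopping treatment "Interruption of study treatment for > 14 days, regardless of reason, from the intended day of the next scheduled dose". Section 6.3.3 makes an exception to the limit for patients who are clearly benefiting.

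**The concern.** Dose-modification tables are followed literally at sites, and here the same laboratory finding leads to two different outcomes. A patient whose enzymes have recovered is either a candidate for restarting or permanently off treatment, depending on which line the investigator reads.

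The table is reached through routine testing. Inclusion criterion 14e, "Serum amylase and lipase", requires values at or below ULN at entry, and the scheduled chemistry panel in Section 7.2.2.6.2 includes both enzymes ("total protein, albumin, bicarbonate, amylase, lipase, total cholesterol").

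The stakes are clinical. Section 5.1 restricts enrolment to patients with no standard option left that is expected to give a durable response, so an unnecessary permanent stop matters to the patient. In the other direction, a patient could be re-exposed whom the stricter row would have stopped.

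**Working it through.** No arithmetic decides this point. The check is to set the two entries side by side and look for text that separates or ranks them.

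| | Hold-and-discuss entry | Discontinue row |
|---|---|---|
| Heading | Asymptomatic amylase/lipase | Asymptomatic amylase/lipase |
| Grade | Any grade 4 | Grade 4 |
| Threshold | Label gives > 5.0 x ULN | > 5.0 x ULN |
| Immediate action | Stop drug | Stop drug |
| After recovery to grade 2 or lower | Restart possible after discussion with the medical monitor | No restart |

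Readings that might reconcile them:

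1. **Symptomatic patients.** The discontinue row stands under the asymptomatic heading. Pancreatitis of grade 2 or higher has its own discontinuation row in the gastrointestinal block.
2. **Recurrence.** The hold-and-discuss sentence covers any grade 4 event, so it already includes a recurrence. The only recurrence rule is for grade 3.
3. **One enzyme each.** The hold-and-discuss sentence names both enzymes, and the discontinue row names neither.
4. **A label displaced in the PDF text.** The hold-and-discuss sentence states grade 4 in its own words. If the label on the discontinue action had moved, that action would have to belong to a neighbour. It does not fit grade 3, which has its own rules, or hyperphosphatemia, which is managed by serum phosphorus in mg/dL.
5. **Worst-toxicity rule (Sections 6.3.1 and 6.3.2, and the table footnote).** It chooses between grades. Here the grade is the same.
6. **Variance clause (Section 6.3.1).** A site following either entry is following the guidelines, so the clause is not triggered.
7. **The 14-day interruption limit.** It does not make the restart option empty: a patient who recovers within the limit may still resume under the first entry.
8. **Amendment 2 summary of changes.** It says the amylase/lipase guidance was updated. It does not say which line should remain.

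None of these settles the conflict.

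**Size.** The only relevant figure is in Section 1.2.1.2.1: "Grade 3 or 4 events that occurred in at least 5% of patients were lipase increased (6.8", in per cent, among 207 phase I patients. 0.068 x 207 = 14.1, so about 14 patients had a grade 3 or 4 lipase increase. Grade 4 is not separated from grade 3, asymptomatic cases are not separated from symptomatic ones, and no amylase figure is given.

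**The case against.** The strongest case for leaving the table alone has four parts.

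- **Layout.** In the text as extracted, the first grade 4 label sits beside the recurrent grade 3 sentence, so row alignment in this block is unreliable. The imaging note just before the discontinue row also omits the word asymptomatic. One could therefore read that row as covering symptomatic grade 4 elevation without diagnosed pancreatitis, which has no row of its own. This is a weak reading: the only heading above the row says asymptomatic, and such a patient is already covered by the row for other clinically significant grade 4 events, which also requires discontinuation.
- **The table only recommends.** The column is headed as recommended modifications. That is so, but two opposed recommendations still leave the site without one.
- **Safety is protected.** This largely stands. A reader might infer that sites could re-expose patients on their own authority. The documents do not support that: the drug stops at once under both entries, and restarting needs recovery to grade 2 or lower and a discussion with the medical monitor, identified as the sponsor's in Section 7.2.2.8.1. The conflict can be caught there. Permanent discontinuation under the second row has no such checkpoint.
- **It is rare.** Possibly, but the documents cannot show it. A reader might apply 6.8% to the planned 70 to 120 patients as a ceiling. That is not supported. The figure covers lipase only, while the table covers either enzyme. The phase I sentence lists only events in at least 5% of patients, so an unlisted amylase event could have any rate below 5%. With no overlap the sum could approach 6.8% + 5% = 11.8%. Even that is no bound, because these are adverse-event rates pooled over doses and schedules, and the phase I rule for reporting a laboratory value as an adverse event is not given.

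A reader might also infer a definite effect on the primary endpoint or on cohort counts. SAP 6.1 does make a patient non-evaluable who had confirmed CR/PR or SD and stopped before week 16 without progression. However, neither the Amendment 3 rationale nor Appendix R (Section 14.1.1.2) ties its use of evaluable to that rule, and the full analysis set contains every dosed patient. No effect on cohort places can be asserted.

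**Conclusion.** The inconsistency is real and should be corrected. For grade 4 asymptomatic amylase or lipase elevation, Table 6-3 both permits and forbids a restart after recovery, and no other text chooses.

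The consequence is limited. The main one without a checkpoint is inconsistent permanent discontinuation of recovered patients. Re-exposure contrary to the stricter row is possible only through the medical monitor. The number affected is unknown, may be zero, and has no ceiling that the documents support. No sample size, power or error-rate figure is affected.

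The conclusion rests on the current table text, and assumes that the discontinue row belongs under the asymptomatic heading, as its position and threshold indicate. It does not depend on which line is a leftover. A reader might infer from the Amendment 2 summary that the discontinue row is superseded text, but that summary does not say so.

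**What to change.** The sponsor confirms which action is intended and leaves exactly one grade 4 entry under the asymptomatic amylase/lipase heading.

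- **If hold-and-discuss governs:** delete the second grade 4 row, the one that requires discontinuation.
- **If discontinuation governs:** delete the grade 4 hold-and-discuss sentence and its label, and keep the sentence on recurrent grade 3.

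The choice is clinical and belongs to the sponsor. The cost is protocol wording only: one row, or one sentence with its label. No analysis or sample size needs to change.

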6.3.3 Criteria for interruption and re-initiation of BGJ398 treatment

If the administration of BGJ398 must be interrupted because of an unacceptable toxicity, BGJ398 dosing will be interrupted or modified according to rules described in [Table 6-3](#).

A patient who requires a dose interruption (regardless of the reason for the interruption) lasting >14 days (counting from the first day when a dose was missed) should discontinue the study treatment unless clearly demonstrating clinical benefit.

Table 6-3 BGJ398 related toxicity management guidelines

Worst Toxicity CTCAE v4.03 Grade (unless otherwise specified)	Recommended Dose Modifications any time during a cycle of therapy
Cardiac disorders	
Cardiac - Prolonged QTcF interval	
Grade 1 and 2 : QTcF \geq 481 msec and \leq 500 msec (asymptomatic)	
Maintain dose level of BGJ398
 
ECG (Electrocardiogram) assessments should be performed for 2 additional cycles at the same frequency as in cycle 1, or as clinically indicated
 
 • If ECG assessments show no QTcF \geq 481 msec, for subsequent cycles ECG monitoring will be performed as per visit schedule. • If ECG assessments are still abnormal (QTcF \geq 481 msec and \leq 500 msec), then ECG monitoring must continue at the same frequency as in cycle 1 for all subsequent cycles.
Grade 3 : QTcF $>$ 500 msec as identified on the ECG by the investigator	
 • Hold BGJ398. • Monitor patient with hourly ECGs until the QTcF has returned to baseline. • Perform further monitoring as clinically indicated. • Exclude other causes of QTcF prolongation such as hypokalemia, hypomagnesaemia and decreased blood oxygenation. • Patients should receive appropriate electrolyte replacement and should not receive further BGJ398 until electrolytes are documented to be within normal limits. • Once the QTcF prolongation has resolved and if the QTcF prolongation was confirmed by the central reader, patients may be re-treated at one lower dose level at the investigator's discretion • ECG assessments should be performed for 2 additional cycles at the same frequency as in cycle 1 or as clinically indicated 
 • If ECG assessments show no QTcF \geq 481 msec, for subsequent cycles ECG monitoring will be performed as per visit schedule. • If ECG assessments are still abnormal (QTcF \geq 481 msec and \leq 500 msec),

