Worst Toxicity CTCAE v4.03 Grade (unless otherwise specified)	Recommended Dose Modifications any time during a cycle of therapy
	
then ECG monitoring must continue at the same frequency as in cycle 1 or as clinically indicated, for all subsequent cycles
 
 Patients who experience recurrent QTcF \geq 500msec after one dose reduction will be discontinued from study. 
NB: If ventricular arrhythmia or Torsades de Pointes is observed in a patient, he/she will be discontinued from the study.
 
Whenever QTcF $>$ 500msec is observed, a plasma sample for determination of BGJ398 concentration should be obtained with the time of sample collection noted.

Cardiac disorders - others Grade \geq 3, or congestive heart failure \geq 2	Discontinue patient from study treatment.
Investigations-Hematology	
ANC decreased (Neutropenia) Grade 3 (ANC $<$ 1.0 - $0.5 \times 10^9/L$)	Hold dose of BGJ398 until resolved to CTCAE Grade \leq 1 or baseline (repeat parameter at least twice a week and as indicated), then 
 If resolved within \leq 7 days, maintain dose level of BGJ398 If resolved within $>$ 7 days, \downarrow 1 dose level of BGJ398.
Grade 4 (ANC $<$ $0.5 \times 10^9/L$)	Hold dose until resolved to CTCAE Grade \leq 1 or baseline (repeat parameter at least twice a week and as indicated), then: 
 If resolved by \leq 7 days after suspending BGJ398, maintain dose level. If resolved by $>$ 7 days after suspending BGJ398, \downarrow 1 dose level.
Febrile neutropenia Grade 3 (ANC $<$ $1.0 \times 10^9/L$, single temperature of $>$ 38.3°C or a sustained temperature of \geq 38.0°C) Grade 4	Hold dose of BGJ398 until resolved to CTCAE Grade \leq 1, then 
 If resolved within \leq 7 days, \downarrow 1 dose level of BGJ398. If not resolved within 7 days discontinue patient from study drug treatment. Discontinue patient from study treatment.

Worst Toxicity CTCAE v4.03 Grade (unless otherwise specified)	Recommended Dose Modifications any time during a cycle of therapy
Hemoglobin Grade 3 (<8.0 mg/dL – 6.5 mg/dL) Grade 4 (< 6.5 mg/dL)	Hold dose of BGJ398 until resolved or corrected to CTCAE Grade ≤ 1 or baseline, then maintain dose level Hold dose of BGJ398 until resolved or corrected to CTCAE Grade ≤ 1 or baseline, then ↓ 1 dose level

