Grade 4	
Discontinue patient from study treatment.
 
Note: Antidiarrheal medication is recommended at the first sign of abdominal cramping, loose stools or overt diarrhea

Vomiting Grade 2 not controlled by optimal anti-emetic therapy Grade 3 not controlled by optimal anti-emetic therapy or Grade 4	
Hold BGJ398 doses until \leq grade 1, \downarrow 1 dose level
 
Discontinue patient from study

Eye Disorders (confirmed by ophthalmologic examination)	
Retinal and Corneal disorders Grade 2 CSR and CSR-like events, Grade 2 Corneal disorder Grade 3 CSR and CSR-like events and any other grade 3 eye disorders \geq grade 1 retinal vein occlusion, grade 4 CSR and CSR-like events, and grade 4 other eye disorders	
Hold BGJ398 until resolved to \leq grade 1 and continue ophthalmologic evaluation
 
 • If resolved within \leq 14 days, \downarrow BGJ398 by 1 dose level • If resolved within $>$ 14 days, discontinue BGJ398 
Hold BGJ398 until resolved to grade \leq 1.
 
 • If resolved within \leq 14 days, \downarrow BGJ398 by 1 dose level • If resolved within $>$ 14 days, discontinue BGJ398 
Discontinue BGJ398

Other ocular/visual toxicity \geq grade 3	
Hold BGJ398 until resolution to \leq grade 1
 
If resolution within \leq 14 days, \downarrow 1 dose level, otherwise discontinue BGJ398

General disorders	
Fatigue Grade 3	
Hold dose of BGJ398 until resolved to CTCAE Grade \leq 1
 
 • If resolved within \leq 7 days, maintain dose level of BGJ398. • If resolved within $>$ 7 days, discontinue patient from study treatment.

Worst Toxicity CTCAE v4.03 Grade (unless otherwise specified)	Recommended Dose Modifications any time during a cycle of therapy
Other clinically significant AEs	
Grade 3	Hold dose of BGJ398 until resolved to CTCAE Grade \leq 1, then \downarrow 1 dose level of BGJ398.
Grade 4	Discontinue patient from study treatment.
All dose modifications should be based on the worst preceding toxicity. Once a dose reduction has occurred, no dose increases can be subsequently implemented. Patients who require more than two dose reductions of BGJ398 will be generally discontinued from study drug treatment.	

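### Table 6-3 does not settle whether BGJ398 may be restarted after a grade 4 eye event that is neither retinal nor corneal and resolves within 14 days

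*Protocol*

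**What the plan says.** Protocol Section 6.3.3 makes the table operative. After unacceptable toxicity, "BGJ398 dosing will be interrupted or modified according to rules described in" Table 6-3, although the action column is headed as recommended.

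Under Eye Disorders, the block labelled for retinal and corneal disorders has three lines:

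- The grade 2 line names CSR and CSR-like events (an eye term here, not the study report) and corneal disorder.
- The grade 3 line reads "Grade 3 CSR and CSR-like events and any other grade 3 eye disorders". The drug is held, then reduced one level if the event resolves to grade 1 or less within 14 days, and discontinued if it takes longer.
- The last line covers retinal vein occlusion of any grade, then "grade 4 CSR and CSR-like events, and grade 4 other eye disorders". The action is to discontinue, with no resolution window.

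A separate row follows for other ocular or visual toxicity of grade 3 or higher. The drug is held until grade 1 or less. If that happens within 14 days, the instruction is to go down "1 dose level, otherwise discontinue BGJ398".

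The general rule at the foot of the table is "All dose modifications should be based on the worst preceding toxicity". The catch-all row, "Other clinically significant AEs", discontinues at grade 4.

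**The concern.** The first block's grade 3 and grade 4 lines speak of eye disorders in general, which is wider than the block's label. The following row is a residual one, but its trigger has no ceiling. Section 8.1.1 does not use grade 5, so that row covers grades 3 and 4. Depending on how far the label reaches, the same grade 4 event falls either under a line that forbids restart or under a row that permits it.

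What is at stake is consistent re-exposure after the highest toxicity grade used in this study. One site could restart the drug and another stop it, each following the table. Section 6.3.1 says "Any planned variance from these guidelines in the view of the patient safety must be previously discussed with the sponsor" unless action is urgent, but a site applying the residual row would not regard itself as varying from the guidelines. Section 12 permits no authorized deviations, yet a monitor could not say whether such a restart was a deviation.

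**Working it through.** No plan figure needs reproducing. The check sets the two sets of instructions side by side for an eye event that is neither a CSR or CSR-like event nor a retinal vein occlusion.

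**Step 1: take each trigger at its full literal scope.** Actions come from Table 6-3; time is time to grade 1 or less.

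| Grade | Resolution | First block | Residual row | Same? |
|---|---|---|---|---|
| 3 | within 14 days | one level lower | one level lower | yes |
| 3 | beyond 14 days | discontinue | discontinue | yes |
| 4 | within 14 days | discontinue | one level lower | no |
| 4 | beyond 14 days | discontinue | discontinue | yes |

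Two grades times two resolution times gives 4 combinations; 3 agree and 1 does not. This shows where a difference is possible. It does not show that both rows apply to the same event.

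**Step 2: give the word other its ordinary residual meaning**, that is, not already covered above. Two readings follow.

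- *Narrow:* the label limits the first block to retinal and corneal disorders. The residual row then takes every remaining ocular event, including grade 4.
- *Broad:* the first block covers all grade 3 and grade 4 eye disorders, as its lines are worded. Nothing is left for the residual row.

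**Step 3: apply both readings to a grade 4 event resolving within 14 days.**

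| Event | Narrow reading | Broad reading |
|---|---|---|
| Retinal or corneal | discontinue | discontinue |
| Neither retinal nor corneal | restart one level lower | discontinue |

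The readings give opposite actions only in the second line.

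**Step 4: look for a tie-breaker.** Sections 6.3.1 to 6.3.4 and the table footer contain no rule of precedence between rows. The worst-preceding-toxicity rule fixes the grade to act on, not the row. The wording points both ways. The narrow reading gives the residual row a function of its own. The broad reading fits the unrestricted terms in the grade 3 and grade 4 lines, which differ from the specific grade 2 line.

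**The case against.** The strongest reply is that the residual row excludes whatever the block above covers, so on any single consistent reading only one row applies and there is no contradiction. That stands, and it narrows the point. A reader might infer that the table gives conflicting orders for every grade 4 eye event other than CSR and retinal vein occlusion. The documents do not support that, because grade 4 retinal and corneal events lead to discontinuation on both residual readings. The reply does not remove the remaining doubt, because the two consistent readings give opposite actions for the other grade 4 events and the text does not choose between them.

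A second reply is that the table was flattened in extraction. Three triggers share one cell and are matched to actions by order, and nearby rows show shifted cells. The caution is fair, but the trigger and action wording of both eye rows is intact, so shifted cells do not explain the doubt.

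A third reply points to safeguards. Eye disorders are to be confirmed by ophthalmologic examination. Section 6.3.4 calls for specialists, ophthalmologists among them, as needed. Section 4.1.1 lets the investigator stop treatment. Events meeting the seriousness criteria reach the sponsor within 24 hours under Section 8.2.2. Under either row dosing stops at onset, and a restart requires recovery to grade 1 or less and a lower dose. These limit the harm and give the sponsor more visibility than Section 6.3.1 alone. They do not tell a site which action the table requires.

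**Conclusion.** The point holds in a narrow form. For a grade 4 ocular event that is neither retinal nor corneal and resolves to grade 1 or less within 14 days, Table 6-3 does not determine whether BGJ398 is stopped for good or restarted one level lower. Grade 3 events, and grade 4 events that take longer than 14 days, end in the same action under both rows.

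This is a minor correction to a safety rule. The documents give no rate for such events, so no patient count is offered. Protocol Section 1.2.1.2.2 describes ocular events as frequent but generally mild to moderate and reversible, so very few patients should be affected. New wording can reach only patients still on treatment or yet to be enrolled; SAP Section 2 (July 2017) says most subjects had already stopped treatment. A reader might also infer a threat to the trial's error rates or primary analysis; nothing here supports that.

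The conclusion assumes that the first block's triggers and actions pair in the order printed.

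**What to change.** Change the trigger of the residual ocular row to grade 3 only, and state that any grade 4 ocular event means discontinuing BGJ398. This agrees with the first block and with the grade 4 action under "Other clinically significant AEs". That support is partial, because the table does allow restart after some grade 4 events. For grade 4 neutropenia, for example, recovery by "7 days after suspending BGJ398, maintain dose level" is the instruction. Once capped, the residual row has the same action as the first block's grade 3 line and could be merged with it.

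If the sponsor intended the narrow scope, this fix would tighten the rule. The alternative is to restrict the first block's grade 4 line explicitly to other retinal or corneal disorders and leave the residual row as it is.

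The cost is a wording change in one row of one table, with no effect on sample size or analysis. The downside of the preferred wording is that a very few patients with fast-resolving grade 4 events lose the option to restart at a lower dose.
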